The benefits of this research are of a scientific nature, which should in the long-term benefit society at large. In particular, the use of ECIGs and heat-not-burn tobacco products has become increasingly popular. There is a lack of information about these products and their effects. The results of this study will inform future work regarding the physiological and subjective effects of ECIG use and heat-not-burn tobacco product use in cigarette smokers.

5. * Describe any potential for direct benefits to participants in this study:
None.

6. Upload a supporting citation list if applicable:

Study Population

1. * Provide the maximum number of individuals that

1. May participate in any study interaction or intervention (including screening, consenting, and study activities)

AND/OR

2. You obtain any data/specimens about (regardless of identifiability)

at VCU and at other sites under the VCU IRB's oversight. See the help text for additional guidance.

75

2. If this is a multi-center project, what is the maximum anticipated number of subjects across all sites?

3. * Provide justification for the sample size by explaining how you arrived at the expected number of participants and why this number is adequate for answering the research questions:

A total of 30 participants will give us the statistical power to examine differences in the physiological and subjective effects of the products. We may consent up to 75 participants in order to obtain 30 participants who complete the entire study.

[Redacted text block]

[Redacted text block]

[Redacted text block]

[Redacted text block]

6. * Will individuals with limited English proficiency be included in or excluded from this research?

- Included
- Excluded - safety concerns if participants are unable to communicate with the study team
- Excluded - instruments/measures only validated in English
- Excluded - no prospect of direct benefit to individual participants
- Excluded - minimal risk study
- Excluded - lack of budget/resources for translation and interpretation [provide an explanation in next question]
- Excluded - other reason [provide an explanation in next question]

7. Justify the inclusion and exclusion criteria if you are either targeting, or excluding, a particular segment of the population / community. Provide a description of the group/organization/community and provide a rationale.

Background, Rationale & Goals Section Complete

Protocol Progress:

- INITIAL SETUP

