4. A detailed description or list of all secondary data elements and/or secondary specimens that will be obtained and how they will be used (if applicable)

See the help text for additional guidance

Participants will first be screened via phone or online, via a multi-study screening process/registry described in HM 20002567 (see attachment "Registry consent form and questions"). Participants can tell study staff if they are interested in screening for a particular study only. All screening data collected from participants who choose to join the registry will be used in this study. Participants who appear eligible will then be scheduled for an in-person screening visit where they will provide informed consent if they choose to participate and complete other forms (see in-person screening forms: ICF, Health Information Form, Penn State Cigarette Dependence Index, and FTND. These will be completed on paper forms or via RedCap). Participants will also be able to view other questionnaires (Direct Effects of Product Questionnaire, Direct Effects of Nicotine Questionnaire, Tiffany-Drobes QSU, Hughes-Hatsukami Questionnaire - listed as Subjectives - 1-4 in documents), via computer, and the study equipment. Women will be excluded if they are breast-feeding or test positive for pregnancy (by urinalysis) at screening. After screening and informed consent, eligible participants will enroll in this study, which is modeled on our previous work (e.g., Spindle et al., 2016). A total of 30 participants are needed to complete the study.

Once enrolled, participants will attend the lab for three additional experimental sessions where they will use the JUUL, IQOS, and own brand cigarettes. Participants will use each of the three products, using one product during a single session. For example, a participant may use the JUUL for the first session, own brand cigarettes for the second session, and the IQOS for the last session. Order of the products used in each session will be assigned using Latin-

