square order procedure, which is similar to random assignment of order. The flavor chosen for the JUUL and IQOS sessions will match their usual brand of cigarettes (tobacco-flavored or menthol-flavored). Participants who enroll in the study at the in-person screening will schedule all of their visits with study staff. These visits may change based on participant and researcher/lab availability, but will follow a schedule described below. Research staff will contact participants over the phone to remind them of upcoming visits and reschedule if necessary.

The sessions will occur no more than 2 days per week and will be separated by at least 48 hours. The approximate total time that participants will be in the laboratory is 12.5 hours (30 minutes for screening and 12 hours for sessions). This does not include the 12 hours before each session that we ask participants to abstain from smoking.

During each session, participants will first complete a 10-puff product use bout, and then a 90-minute ad lib product use bout (each session will be approximately 3 hours). Sessions will be preceded by 12 hours tobacco/nicotine abstinence and an in-person 1-hour waiting period (to help ensure nicotine abstinence) to measure the extent to which each device suppresses nicotine/tobacco abstinence symptoms; and session order will be ordered by Latin-square. Other outcomes include plasma nicotine, carbon monoxide levels, cardiovascular response, and subjective effects (direct effects of the product and nicotine, abstinence symptoms, acceptability, as in Blank et al., 2009).

More specifically, upon arrival at the laboratory for each session, participants' breath CO will be measured to ensure compliance with the overnight abstinence criteria (i.e. CO < 10 ppm; see Breland et al., 2006). The session will then begin with a 1-hour waiting period (to help ensure nicotine abstinence). After this waiting period, an IV catheter will be inserted into a forearm vein of the participant, physiological monitoring equipment will be attached (arm blood pressure cuff, pulse oximeter placed on finger), and the session will begin. A detailed timeline of the sessions is described below. Please note that because catheter insertion can be difficult, we will attempt to insert a catheter no more than three times in one day, and if all three attempts are unsuccessful, the session will be discontinued, with payment as outlined in the consent and compensation section.

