In addition, non-invasive computerized monitoring equipment allows for minute-by-minute, real time monitoring of participants' heart rate and blood pressure (BP). Research personnel are trained to alert the research nurse if heart rate exceeds 120 beats per minute, if systolic BP exceeds 150 mm Hg, or if diastolic BP exceeds 100 mm Hg. Individuals whose heart rate and/or BP levels remain elevated will be monitored continually by the nurse, and if necessary emergency responders will be notified. Emergency medical coverage is available via the emergency room that is a half block away from the CBPL. The ER is approximately 1.5 miles away from the new laboratory location of the CSTP.

In the case of nicotine abstinence symptoms, the project products will possibly alleviate these risks. Participants will be provided with water at all times.

The risk of seizures is minimized by excluding participants with any history of seizures, and by having a full-time RN available, as well as monitoring of vital signs. In addition, some of the reported seizures occurred in users who were using other substances such as marijuana or amphetamines—the risk of seizures in this study is reduced as we are administering nicotine and no other substances.

Participants will be able to view all questionnaires used in sessions before attending sessions, and will be informed of the length of each session. If participants do not want to answer the questionnaires, or feel that the length of the sessions will be too long, they can choose to not participate.

Risk of loss of confidentiality will be minimized by only connecting participant data to participants by alpha numeric identifiers. These data can only be linked with identifiable information by using a key that is stored in locked cabinets. Research staff will also not release any participant study information to others without signed written approval from a participant.

3. * Describe any potential risks or harms to a community or a specific population based on study findings (e.g. information that could be stigmatizing or derogatory):
None.

4. Where appropriate, discuss provisions for ensuring necessary medical, professional, or psychological intervention in the event of adverse events to the subjects:

Individuals whose heart rate and/or BP levels remain elevated will be monitored continually by the nurse and if necessary, emergency responders will be notified. Emergency medical coverage will be available via the emergency

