room that is a half block away from the CBPL. The ER is approximately 1.5 miles away from the new laboratory location of the CSTP.

5. * Describe criteria for when the investigator would withdraw an individual participant from the study; such as safety or toxicity concerns, emotional distress, inability to comply with the protocol, etc.:
- Participants may be withdrawn from the study if the PI or study nurse has any safety concerns (such as continuous high blood pressure or heart rate) during sessions, or if an intravenous catheter cannot be successfully inserted.
6. * Summarize any pre-specified criteria that would trigger the investigator/sponsor/monitoring committee to stop or change the study protocol due to safety concerns:
- At this time we do not have a pre-specified criteria for stopping or changing the study protocol due to safety concerns.

Data and Safety Monitoring

Data and safety monitoring is a system for checking the study's data at regular intervals over the study period to identify and address issues that could affect the safety of research participants. This requirement is in accordance with 45 CFR 46.111.

The purpose of data and safety monitoring plan is to set forth study team procedures for monitoring/addressing:

- Participant safety (physical, psychological, etc.)
- Data validity
- Early stopping (termination) based upon changes in risks and benefits.

7. * Indicate if this study will have a Data Safety Monitoring Board (DSMB) or a Data Safety Monitoring Plan (DSMP): [Required for all greater than minimal risk studies]

- DSMB
- DSMP
- No DSMB/DSMP [Note: This response is not applicable for greater than minimal risk studies]

ID: HM20012013

View: SF2 - Privacy

Privacy

Privacy refers to an individual's right to control how others view, record, or obtain information about them. When privacy is violated it can involve such things as

- Being asked personal questions in a public setting;
- Being publicly identified as having a particular characteristic or diagnosis;
- Being seen entering a place that might be stigmatizing;
- Being photographed, videotaped or observed without consent;
- Disclosure of personal information to unauthorized people

Privacy is not the same as confidentiality because privacy protections apply to people, and confidentiality protections apply to data. Confidentiality protections should be described on the Data Confidentiality page of this form, not here.

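### Does aiming for 30 completers, while allowing withdrawal for high heart rate or blood pressure, select the strongest cardiovascular responders out of the results?

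*Protocol*

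**What the plan says.** Study Population, item 3, justifies the sample size in two sentences. The first states that "A total of 30 participants will give us the statistical power to examine differences in the physiological and subjective effects of the products"; the second is "We may consent up to 75 participants in order to obtain 30 participants who complete the entire study". Study Procedures, item 7, repeats the target: "A total of 30 participants are needed to complete the study". The design is a three-session crossover: "Participants will use each of the three products, using one product during a single session". The same item lists the outcomes: "Other outcomes include plasma nicotine, carbon monoxide levels, cardiovascular response, and subjective effects".

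Risks, Discomforts, Potential Harms and Monitoring, item 5, permits but does not require withdrawal where either the nurse or the investigator "has any safety concerns (such as continuous high blood pressure or heart rate) during sessions, or if an intravenous catheter cannot be successfully inserted". Item 2 of that section describes what happens first. The instruction to staff reads: "alert the research nurse if heart rate exceeds 120 beats per minute, if systolic BP exceeds 150 mm Hg". A diastolic alert limit of 100 mm Hg applies as well. For values that stay high it provides for continued observation by the nurse and, if needed, a call to emergency responders.

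Data Retention, item 3, describes removal of a participant's data when that participant asks for it. The protocol describes no other route by which collected data leave the study.

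**The concern.** Three statements, read together, suggest a selection problem. The stated power is tied to 30 people who finish all three sessions. Anyone who leaves early does not count towards the 30 and is in effect made up by further consenting. One named ground for ending participation is a high value of a measured outcome. If the 30 completers were also the analysis set, whether a person is analysed would depend partly on how that person reacted to a product. A similar argument can be made for someone who finds a product unpleasant and leaves, with subjective ratings as the outcome.

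At stake would be understated cardiovascular effects, product differences pulled towards zero, and the loss of usable within-person information from one or two completed sessions.

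**Working it through.** **1. What the 30 and the 75 are.** 30/75 = 40%, so the ceiling allows 60% of those consented not to complete; conversely 30/(1 − 0.60) = 75. That 60% is not post-enrolment loss. Study Population, item 1, counts everyone who is screened or consented, and consent is taken at the in-person screening visit (Consent Process). Loss after product use cannot be separated from screen failure. The figure of 30 itself cannot be reproduced, because no alpha, effect size or SD is given.

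**2. Is a completer-only analysis stated?** The concern needs three links: completers are the target, exit can depend on the outcome, and only completers are analysed. The first is in the protocol. The second is there as a possibility. The third is absent: there is no analysis set, no complete-case rule and no statement that partial data are dropped. A target of 30 completers is fully compatible with analysing everyone who started a session.

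**3. How strong is the link from outcome to exit?** Withdrawal is discretionary, and sustained elevation is one example of a safety concern. Crossing an alert limit brings in the nurse; it does not end participation. The limits are absolute levels, not changes from baseline. The other named ground, failed catheter insertion, arises before product use in that session.

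**4. Size if only completers were analysed (assumed values throughout).**

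*Truncation of one product's mean.* Removing the top fraction p of a normal response lowers its mean by φ(z)/(1 − p) SD: 0.109, 0.195 and 0.350 for p = 5%, 10% and 20%. These loss rates have no source in the protocol. The calculation also moves one product only, whereas a completer analysis drops the person from all three. With equal SDs and within-person correlation ρ, the contrast shifts by (1 − ρ) times these values. At an assumed ρ = 0.5 that is 0.054, 0.098 and 0.175 SD.

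*Simulation on the level.* One million participants with three sessions each; a participant is lost if any session exceeds the alert level, with a set probability per exceedance. The alert levels stand in for a withdrawal threshold that the protocol does not give.

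- Heart rate above 120 bpm; baseline 70, SD 8 to 12; product rises 15/12/8, SD 6, correlation 0.5; probability 0.5 or 1.0. Withdrawn: 0.02% to 0.54%. The largest mean falls from 15 to 14.97 at worst, and the contrast of 7 to 6.99.
- Systolic pressure above 150 mm Hg; product rises 10/8/5, SD 7, correlation 0.5:

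| Baseline mean (SD) | Probability per exceedance | Withdrawn | Largest mean (true 10) | Contrast (true 5) | Contrast (true 2) |
|---|---|---|---|---|---|
| 120 (10) | 0.1 | 1.0% | 9.94 | 4.99 | 2.00 |
| 120 (10) | 1.0 | 6.8% | 9.55 | 4.87 | 1.93 |
| 125 (12) | 0.5 | 12.0% | 9.43 | 4.90 | 1.94 |
| 130 (12) | 0.1 | 5.3% | 9.82 | 4.99 | 2.00 |
| 130 (12) | 1.0 | 28.6% | 8.69 | 4.67 | 1.82 |

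The worst case loses (10 − 8.69)/10 = 13% of the largest mean, (5 − 4.67)/5 = 7% of the larger contrast and (2 − 1.82)/2 = 9% of the smaller. Across scenarios, those withdrawn have a mean baseline of about 136 to 145 mm Hg, against about 119 to 129 in those kept. The trigger therefore selects mainly on baseline.

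*Scale.* With 30 pairs, 80% power and an assumed two-sided 0.05, the detectable paired standardised difference is 0.53. In this simulation the variance of a product difference is 2 × 7² × (1 − 0.5) = 49, so its SD is 7 mm Hg and the detectable difference is 0.53 × 7 = 3.7 mm Hg. The worst contrast loss is 5 − 4.67 = 0.33 mm Hg.

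**The case for a change.** The best case for the concern is that the protocol ties power to no count other than full completers, and that a measured outcome can end participation. Each session is informative in a crossover, and vital signs are monitored minute by minute, so the values leading to a withdrawal would be on record. A model using all data up to withdrawal would handle this well, while a completer analysis might not. Saying so would cost one sentence.

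Two parts of this stand. The design does allow outcome-related exit, and an analysis confined to completers would tend to understate cardiovascular effects. But that is a condition the protocol does not set. The suggested additions are an analysis set, a mixed model, a completer sensitivity analysis and withdrawals listed by product and reason. All of these are ordinary analysis-plan content, and they would leave both the withdrawal wording and the target of 30 untouched. They correct nothing the protocol states.

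The argument about disliked products is possible but has no figure behind it. Payment rises from $75 to $100 to $125 across the sessions (Compensation, item 1), which favours completion. Blood pressure is also assessed at screening (Pertinent and Incidental Findings, item 2). Text after the sample-size answer is redacted, so whether a pressure limit applies at entry cannot be seen.

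**Conclusion.** The concern does not hold. The protocol sets a recruitment target and a consent ceiling; it does not say that only completers are analysed or that data from withdrawn participants are discarded. Without that step, outcome-related withdrawal does not by itself select anyone out of the results.

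Were the analysis confined to completers, the effect under the assumed values would be negligible for heart rate. For systolic pressure it would be 0% to 13% of the largest product mean and 0% to 9% of a contrast, the upper ends requiring withdrawal at every exceedance and a high baseline. These figures rest on assumed means, SDs, a correlation of 0.5 and the alert levels used as a stand-in threshold, so they show the order of magnitude only. How partial data are handled is a question for the statistical analysis plan. No view is taken on the withdrawal rule or the alert limits.

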The subjective questionnaires administered at each time point are as follows: Direct Effects of Product Questionnaire, Direct Effects of Nicotine Questionnaire, Tiffany-Drobes QSU, and the Hughes-Hatsukami Questionnaire. All of these questionnaires will be administered via RedCap or paper and pen.

Experimental session timeline (times approximate):

Participant arrives, CO test to confirm tobacco abstinence,

1-hour waiting period, then the rest of the session will begin, as described below.

0 Hr 0 min - Attach physio equipment, insert catheter administer Subjectives - 1

0 Hr 30 min Blood draw #1 and record Carbon Monoxide

0 Hr 35 min 10 puffs from product (30s inter-puff interval)

0 Hr 40 min Blood draw #2

0 Hr 45 min Record Carbon Monoxide, Subjectives - 2

1 Hr 05 min Blood draw #3, record Carbon Monoxide, Subjectives - 3, ad lib use period begins

2 Hr 35 min Blood draw #4 (ad lib period ends)

2 Hr 40 min Record Carbon Monoxide, Subjectives - 4

2 Hr 45 min Remove Catheter, Stop Physio Monitoring

Payment

Release

8. * The IRB only reviews research procedures, so differentiate which of the study procedures are:

- Being performed exclusively for research purposes (i.e. they would not otherwise be done apart from this study).
 - Alterations of routine procedures (e.g. the study is altering the timing, frequency, method, location, amount, etc.).
 - Being done for other purposes and whose data/results will be used secondarily in the study (e.g. standard medical or psychological tests, routine education practices, quality improvement initiatives, etc.).
- All procedures are performed exclusively for research purposes.

9. If applicable, describe alternatives (research or non-research) that are available to potential participants if they choose not to participate in this study:

10. Upload any supporting tables or documents (e.g. protocol documents, figures/tables, data collection forms, study communications/reminders):

Upload ALL instruments/guides that will be used or that participants will experience (i.e. see, hear, complete), including measures, scripts/questions to guide interviews, surveys, questionnaires, observational guides, etc.:

Upload ALL recruitment and screening materials, including such as ads, flyers, telephone or in-person scripts, letters, email invitations, Telegram announcements, and postcard reminders, screening scripts, screening forms, and screening measures:

ID: HM20012013

View: SF2 - Project Details

Project Details

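### Does giving the Direct Effects of Product Questionnaire before any product is used spoil the product ratings?

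*Protocol*

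**What the plan says.** All of the relevant text is in the Protocol, Study Procedures, item 7, with one related statement under Sample Collection Details.

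- **Which forms, when.** "The subjective questionnaires administered at each time point are as follows: Direct Effects of Product Questionnaire", and the sentence goes on to name three more: a nicotine-effects questionnaire, the QSU and a fourth instrument. No time point is excepted.
- **First assessment.** "0 Hr 0 min - Attach physio equipment, insert catheter administer Subjectives - 1".
- **First product use.** "0 Hr 35 min 10 puffs from product (30s inter-puff interval".
- **First assessment after use.** "0 Hr 45 min Record Carbon Monoxide, Subjectives - 2". Two more follow, Subjectives-3 at 1 h 05 min and Subjectives-4 at 2 h 40 min.
- **State at arrival.** "Sessions will be preceded by 12 hours tobacco/nicotine abstinence and an in-person 1-hour waiting period".
- **Labels.** In the description of the screening visit the four questionnaires are "listed as Subjectives - 1-4 in documents". In the session timeline the same label, with numbers 1 to 4, marks four time points.

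Direct effects of the product appear in a parenthesis among the other outcomes. No baseline, change score or model is given for them. Under Sample Collection Details, item 5, a change before and after bouts is stated for carbon monoxide only. The questionnaire items are not reproduced in the text.

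**The concern.** A person who has been abstinent for 12 hours, has waited another hour and has not yet touched the session's product cannot report that product's effects. The answer would be a zero, a guess, or a memory of another product or session. The nicotine-effects, craving and abstinence questionnaires can be answered sensibly at that moment; the product questionnaire is the odd one out.

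Subjective effects are one of the four things the study sets out to compare, and the justification for 30 completers mentions them. If the first score entered the analysis as a fourth level of time, the estimated product difference would look smaller. If it were subtracted as a baseline, it could add noise and cost power.

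The double use of the label adds to the worry. If the screening-visit label meant the instruments in the order listed, and that meaning were carried into the timeline, the product questionnaire would be given only once, before use.

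**Working it through.** **Schedule.** Subjectives-1 is at 0:00 and the first puff at 0:35, so the first form precedes use by 35 minutes. Subjectives-2, -3 and -4 (0:45, 1:05, 2:40) all follow use. One of the four product ratings has no referent in the session; three do. This part of the concern is correct.

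**Label.** The sentence just before the timeline gives all four instruments at each time point. That rules out a schedule in which each numbered slot holds a single instrument. The label is duplicated, but the schedule can still be read.

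**Effect on a product contrast.** The Protocol gives 30 completers but no alpha, power, effect size or SD, so there is no planned figure to reproduce. The rest is illustration on assumed inputs: a paired contrast between two products, n = 30, two-sided alpha 0.05, post-use difference δ with SD 1, and power from the noncentral t distribution with 29 degrees of freedom and noncentrality (δ/SD) × √30.

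*Case 1: pre-use answers at a constant floor of zero.*

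- Averaging all four times multiplies every person's three-time mean by 3/4. The difference becomes 0.75δ and its SD becomes 0.75, so δ/SD = 0.75δ/0.75 = δ. The estimate shrinks on paper, but the t statistic and power do not move.
- Subtracting a constant leaves the post-use score unchanged apart from that constant, so again nothing changes.
- For δ = 0.5, power is 75% with or without the first score.
- In a simulation of 4000 trials with no product effect (3 products × 4 times), the interaction test rejected in 5.7% with the first score fixed at zero and 5.4% with an ordinary baseline. With the Greenhouse-Geisser correction it was 4.0% in both.

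*Case 2: pre-use answers are independent noise with SD s in each session.*

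- Change score: SD of the difference = √(1 + 2s²).
- Four-time mean: difference 0.75δ, SD = √(9 + 2s²)/4.

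| s | SD of change difference | Power, change score (δ = 0.5) | SD of four-time-mean difference | Power, four-time mean (δ = 0.5) |
|---|---|---|---|---|
| 0 | 1.000 | 75% | 0.750 | 75% |
| 0.25 | 1.061 | 70% | 0.755 | 75% |
| 0.5 | 1.225 | 58% | 0.771 | 73% |
| 1.0 | 1.732 | 33% | 0.829 | 67% |

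For δ = 0.4 the change-score powers are 56%, 52%, 41% and 23%; for δ = 0.6 they are 89%, 85%, 74% and 45%. The noise costs precision but does not bias the contrast.

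*Case 3: equal variance before and after use, change score.* The variance of a change is 2(1 − ρ) times that of a single score.

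- A contrast with dz = 0.529 has 80% power on post-use scores.
- With ρ = 0, dz = 0.529/√2 = 0.374 and power is 51%.
- With ρ = 0.3, dz = 0.529/√1.4 = 0.447 and power is 66%.

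These losses need two things together: pre-use answers as variable as real ratings, and an analyst who subtracts them. Answers that variable are also incompatible with the zeros behind the 3/4 figure, so the two harms cannot be added.

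**The case for a change.** The best case for a change is that this is a rule about data collection, not analysis. The Protocol itself fixes which forms are completed when. A later analysis plan could discard the first score but could not say what it referred to. The form also asks for enough detail to replicate the methods, and a reader meets one label with two meanings. Products are visible to participants, so a pre-use answer might reflect expectation about a familiar cigarette against an unfamiliar device. Such answers would differ by product and would bias a change score. The cure is cheap: a sentence, and one form fewer in each first packet.

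The wording point stands: the sentence is looser than it should be, and the label is used twice. The bias argument is possible, but it again needs the pre-use score to serve as a baseline, which the Protocol does not propose. It also depends on item wording that is not shown; the first packet may omit or adapt the product items. An unneeded form displaces none of the post-use ratings, and setting it aside is an ordinary analytic decision that can be left to the statistical analysis plan.

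**Conclusion.** The observation is correct, but the harm is not shown. Taken literally, the Protocol collects one uninterpretable product rating per session, 35 minutes before use, alongside three interpretable ones. It commits to no analysis that uses the first.

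Under the simplest assumption, a common floor before use, the loss is nil: the standardised contrast and its power are identical, and the error rate of the interaction test is essentially unchanged. Averaging the first score in costs little unless it is very noisy: from 75% to 67% at worst among the values examined at 0.5 SD. The larger figures, 51% in one illustration and 33% in the other, require a change-score analysis that the Protocol does not state and noise levels that it gives no reason to expect.

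All the power figures rest on assumed effect sizes, SDs and correlations. The conclusion rests less on them than on two facts in the text: every post-use rating is collected, and the pre-use one can be left out without loss. This is a clerical looseness that analysts fill sensibly, and no change to the plan follows.

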- The procedures that will be followed to collect the sample
- The role(s) of the individuals who will collect the sample
- The volume/size range of the sample
- The timing and frequency of sample collection

Urine will be collected at screening to test for pregnancy (women only). Urine will not be stored for later use.

Upon arrival at the CBPL/CSTP for the research session, participants' breath CO will be measured to ensure compliance with the overnight abstinence criteria (i.e. CO < 10 ppm; see Breland et al., 2006). CO will also be measured before and after bouts to be analyzed as a study outcome measure (change in CO before and after bouts).

Blood will be collected via intravenous catheter 4 times at each session (7 ml each time), for a total of 12 samples per person in the entire study (84 ml in total). Blood will not be collected more than 2 times per week.

6. * Will genetic testing or analyses be conducted on any of the samples:

- Yes
- No

ID: HM20012013

View: SF2 - Active Internet Data Collection

Active Internet Data Collection

1. * Describe the platform/technology chosen for collecting the data and transmitting data securely over the Internet. Give the rationale for selecting this technology.

The in-person screening questionnaires and questionnaires administered during sessions may be administered via RedCap or via paper forms. All of the data will be stored in REDCap, and viewing will be restricted to those personnel associated with this protocol (listed under personnel).

2. * Describe how data will be linked or unlinked to identifiers including email addresses, names, and/or IP address.

Data will be linked (via a key stored in a separate location) to participant IDs and dates of birth.

3. * Is there an alternative method for completion of the data collection other than the Internet?

- Yes
- No

4. * If yes, describe the alternative(s).

Paper forms.

5. * Describe how individuals will be able to skip or not answer particular questions. If any questions are mandatory, provide justification.

Participants will be able to skip any question.

6. If not including children, describe any procedures used to verify that research participants are adults.

We ask participants for their age and date of birth several times (telephone or online screening, in-person screening) and verify that the answers are the same.

ID: HM20012013

View: SF2 - Secondary Data/Specimen Details

Secondary Data/Specimen Details

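### Does taking the ad lib CO change from the 1:05 reading, after 10 puffs of the same product, spoil the own-brand versus device comparison?

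*Protocol*

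**What the plan says.** The protocol describes CO as an outcome in two places.

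- Sample Collection Details, item 5, which asks how and when samples are taken: CO readings around the bouts are "to be analyzed as a study outcome measure (change in CO before and after bouts".
- Study Procedures, item 7: "Other outcomes include plasma nicotine, carbon monoxide levels, cardiovascular response, and subjective effects".

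The experimental session timeline in Study Procedures gives the readings:

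- "0 Hr 30 min Blood draw #1 and record Carbon Monoxide", before any product is used.
- "0 Hr 35 min 10 puffs from product (30s inter-puff interval", followed by a CO reading at 0:45.
- "1 Hr 05 min Blood draw #3, record Carbon Monoxide, Subjectives - 3, ad lib use period begins".
- "2 Hr 40 min Record Carbon Monoxide, Subjectives - 4", five minutes after ad lib use ends at 2:35.

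Only one product is used in a session. On arrival at every session, "participants' breath CO will be measured to ensure compliance with the overnight abstinence criteria (i.e. CO < 10 ppm". The protocol gives no formula for the change, does not name the reading that serves as the ad lib baseline, and states no model. It gives no CO clearance rate and no CO yield for any product.

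**The concern.** Four scheduled readings and two bouts suggest two before-and-after pairs: 0:30 with 0:45, and 1:05 with 2:40. On that reading the second baseline is not free of treatment. It comes about 25 minutes after 10 puffs of the very product being compared. If own-brand cigarettes raise CO in the first bout and a device does not, the own-brand baseline is higher, and part of it clears before 2:40. The subtraction then takes away more than it should in the own-brand session, and the contrast shrinks.

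The comparison of each device with own brand is the study's stated purpose, so a distortion there would matter. Two further worries follow. A session with a product that yields no CO would show a fall. And a plain change score might be less precise than an analysis adjusted for the product-free 0:30 reading.

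**Working it through.** **Timing (session timeline).** Ten puffs at 30 s intervals last 9 × 30/60 = 4.5 to 10 × 30/60 = 5 minutes. The first bout therefore runs from 0:35 to about 0:40. The 1:05 reading is about 25 minutes later, and 2:40 is 95 minutes after 1:05.

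**Assumptions (none is in the protocol).** First-order clearance with half-life T of 3 to 5 h; first-bout CO still present at 1:05 in the own-brand session, b, of 2 to 8 ppm; a device that adds no CO. Let A be the CO from ad lib use present at 2:40.

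**Share cleared from 1:05 to 2:40:** f = 1 − 0.5^((95/60)/T).

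| T | f | b × f at b = 2 | b × f at b = 8 |
|---|---|---|---|
| 3 h | 0.306 | 0.61 ppm | 2.45 ppm |
| 4 h | 0.240 | 0.48 ppm | 1.92 ppm |
| 5 h | 0.197 | 0.39 ppm | 1.58 ppm |

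**Contrast with 1:05 as baseline.** Own brand minus device = A − bf. The shortfall of 0.39 to 2.45 ppm is 3 to 25% of a true A of 10 to 15 ppm, and 8 to 49% of an A of 5 ppm. The worst case in this range leaves 5 − 2.45 = 2.55 ppm, so the sign holds. Widening the half-life to 2 h gives f = 0.422 and, at b = 8, a shortfall of 3.38 ppm; 5 − 3.38 = 1.62 ppm, still positive.

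**Contrast with 0:30 as baseline.** Own brand minus device at 2:40 = A + b(1 − f), because the uncleared first-bout CO is still there. As a measure of A it is too high by 0.69b to 0.80b, against 0.20b to 0.31b too low with 1:05. The ratio of the two errors is (1 − f)/f, about 2.3 at 3 h and 4.1 at 5 h. Example with T = 4 h, b = 5, A = 10:

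- from 1:05: 10 − 5 × 0.240 = 8.8 ppm
- from 0:30: 10 + 5 × 0.760 = 13.8 ppm

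If the target is instead the combined effect of both bouts, 0:30 gives it exactly and 1:05 falls short by (A + b(1 − f)) − (A − bf) = b.

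**The fall with a no-CO product.** A 1:05 reading of 5 to 8 ppm would drop by 1.0 to 2.4 ppm. That is real clearance of CO left from before the session. It occurs in all three sessions under the same arrival limit, so it cancels in expectation from the within-participant contrast.

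**Precision.** With equal variances, covariate adjustment has (1 + r)/2 of the change-score variance: 65 to 85% for r = 0.3 to 0.7. That holds only if both methods use the same baseline. Replacing 1:05 with 0:30 makes the ratio (1 − r0²)/(2(1 − r1)), where r0 and r1 are the correlations of the 2:40 value with the 0:30 and 1:05 values:

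- r0 = 0.3, r1 = 0.7: 0.91/0.60 = 1.52, worse than the change score
- r0 = r1 = 0.5: 0.75/1.00 = 0.75, better

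Nothing in the protocol settles which applies. Equal variances are also doubtful, since CO on arrival is capped below 10 ppm and CO after ad lib smoking is not.

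**The case for a change.** The strongest case for a change is this. The protocol names the CO outcome itself, so the point is not purely a matter for an unseen analysis plan. The schedule makes 1:05 the natural baseline for ad lib use, and that reading does follow use of the product under comparison. The device comparison is the study's aim, CO bears on the reduced-exposure claims mentioned in the background, and one sentence would settle the definition using data already collected.

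The timing and the direction of the effect stand. The rest is weaker. The wording comes from an item about collecting samples and does not commit the analysts to an unadjusted difference from 1:05; Study Procedures lists CO levels, which leaves an analysis of levels by time point open. Taking the reading at the start of a bout as that bout's baseline is a legitimate way to separate the two bouts. Treating it as an error presumes a cumulative effect as the target, which the protocol does not state. Nor is there reason to carry the argument over to plasma nicotine, which is nowhere defined as a change.

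**Conclusion.** No change to the protocol follows. A change from 1:05 would make the ad lib own-brand excess modestly conservative, by 0.39 to 2.45 ppm if the half-life is 3 to 5 h and 2 to 8 ppm of first-bout CO remains at 1:05. Both figures are assumptions, and the calculation also supposes a device that adds no CO. The effect matters most if the true ad lib rise is small (up to 49% of 5 ppm), but it did not reverse the contrast, and the 0:30 to 0:45 contrast is unaffected.

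Moving to 0:30 exchanges an incremental ad lib effect for a cumulative one. It is not a correction, and a gain in precision is not assured. Which of the two is reported, and with what model, is detail that analysts normally state in the analysis plan, and the four scheduled readings support either. A reader of an incremental result need only bear in mind that clearance pulls it toward no difference.
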